## **D2. Collaboration**

The investigators have established collaborative agreements with six mental health provider organizations who serve large numbers of adolescents with moderate to severe externalizing behavior problems (see Letters of Support in Appendix 1). These organizations provide mental health services to this population using a range of treatment modalities. Youth are generally allocated to a particular level of service based on problem severity. For example, an adolescent engaging in truancy and rule-breaking behavior may be offered participation in once-weekly multiple family group therapy (i.e., several parent-youth dyads meet together for improved parental management of behavior); a youth abusing substances may receive once-weekly individual and once-weekly dyadic (parent-youth) outpatient sessions; and youth with criminal arrest histories may receive multiple in-home family-therapy oriented treatment sessions each week (i.e., Multisystemic Therapy). These modalities are reflective of current standards of care for youth with varying severities and types of externalizing behavior problems. A common component of each of these modalities is a strong emphasis on parental involvement in treatment and a focus on improving parental management of youth behavior, consistent with the empirical literature regarding what makes treatments for youth externalizing behavior problems effective.

Our partner organizations, located across the U.S., are as follows: Advanced Behavioral Health (ABH; Connecticut); Catholic Charities (Western New York State); Children's Village (New York City and New Jersey); the Maryland Innovations Institute (Maryland); the Portland DBT Institute (PDBTI); and the University of Washington Public Health and Justice Policy Center. Collectively, these organizations employ over 200 mental health therapists who serve youth with externalizing and other behavior problems. We will recruit therapists, parents, and youth to participate in the study from this pool.

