Phone-based data collection (i.e., automatic app usage data and self-report daily satisfaction ratings) will cease the day after the last day of the testing period (i.e., day 15 or day 46, depending on group).

**Instructions for using the app.** Verbal instructions for how to use the app will be provided to parents as part of their baseline assessment session (see Parent and Youth Baseline Assessment Section, above). These instructions to parents will vary, depending on whether the parent is participating in the Field Test or the Open Trial. Those parents in the **Field Test** will be encouraged to use the app as much as possible over the next 2 weeks. These parents will be told that the purpose of this phase of app usage testing is to debug any remaining problems with the app, and so the research staff would greatly appreciate it if they made an effort to use the app every day and to explore all of its features. These parents will also be instructed to encourage the youth to use the app as much as possible during this period.

Parents participating in the **Open Trial** will be told that they should use the app in whatever ways they wish and using whatever degree of clinical support from the therapist all parties (parent, youth, and therapist) deem necessary or helpful.

**Post-usage assessment battery and exit interview.** When calling to schedule or to confirm a scheduled post-usage assessment session, research staff will inform parents that each participant's timely completion of the session (i.e., within 2 weeks of the testing period ending) will earn the participant an additional raffle ticket for the tablet computer lottery.

On or about day 15 (for Field Test participants) or 46 (for Open Trial participants), the parent and youth each will complete the post-usage assessment session, by phone or in person (most are expected to occur by phone). In these sessions, the same battery of questionnaires related to clinical targets will be administered (on paper or using RedCap), plus several questionnaires related to satisfaction with and acceptability of the app. The session will conclude with a 30-45 minute open-ended "exit" interview with a member of the research staff during which the participant will have an opportunity to share thoughts and opinions about the experience of using the app and offer any suggestions for improvement.

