**D 6.2. Measures: Parents and adolescents.** Enrolled parents and adolescents will generate 4 types of data: a) self-report questionnaires administered before (pretest) and after (post-test) the app usage period; b) app usage data, generated by the app whenever the parent or adolescent uses it and automatically stored on the app's server; c) daily app satisfaction ratings, prompted by the app, completed directly on the phone, and stored on the app server; and d) an open-ended qualitatively-oriented exit interview.

**Self-report questionnaires.** Tables D6.2a and D6.2b outline the measures that will be administered to enrolled parents and youth, respectively, at pre- and/or post-usage assessment points. Full questionnaires are provided as Appendices 12 and 13 to this protocol. Measures pertaining to participant functioning and parenting behavior are all commonly used in studies with populations similar to those in the present study (adolescents presenting to treatment and their families), including intervention outcome studies, and are psychometrically sound (i.e., good reliability and predictive validity). Additional psychometric information about these measures is available upon request. With the exception of the history of arrest questions (collected for descriptive purposes), these measures are expected to show improvements over time as a result of VillageWhere app usage for those participants in the open trial.

A family demographics measure, administered only to parents, was created for this study in order to describe the sample. The System Usability Scale ([name] et al., 2009) is commonly used in product development studies and relates to the user's satisfaction with and opinion of the acceptability of VillageWhere. A brief technology use and comfort questionnaire was created for this study.

Note that any measure listed at only the pre- or post-time point will only be administered at that time point. All measures will be entered into the RedCap system for data collection.

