## **D11. Data Analysis**

Data from demographics questionnaires and the Technology Use and Comfort Survey will be used to describe the sample itself. App usage and SUS data will be used to describe the success of the app itself. On the SUS, scores below a 3.5 on a five-point Likert scale (1 = poor; 2 = fair; 3 = good; 4 = very good; 5=excellent) will indicate a need for further app refinement in subsequent research. An aggregated mean score of 3.5 or higher will support app feasibility. App usage data will be aggregated and subjected to descriptive analyses to determine most preferred features and feature use sequences. Correlational analyses will link app usage data to participant satisfaction ratings and to measures of parent/youth behavior and functioning, to determine if certain app features were more highly preferred or more linked to changes in functioning than others.

Average scores on the SUS will also be compared between parents and adolescents. Between-group comparisons on the USAS will involve independent samples t-tests; effect size estimates also will be computed.

Pre- to post-usage change will be assessed on all parent and youth measures of functioning and behavior. Paired-samples T tests will be used and effect sizes obtained.

Qualitative data obtained from exit interviews will include annotations from investigators noting likes, dislikes, points of confusion, suggestions for improvement, misunderstandings, and potential unintended consequences. Qualitative data will be analyzed using a grounded theory approach (a data-reduction method for qualitative data used to generate and test hypotheses from the ground up).

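### D11 correlates self-selected app use with functioning, with no baseline adjustment and no stated outcome score, so a link between use and baseline severity (if there is one) can produce spurious feature-outcome associations

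*Combined protocol and SAP*

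**What the plan says.** D11 describes the analysis of use against outcome in one sentence: "Correlational analyses will link app usage data to participant satisfaction ratings and to measures of parent/youth behavior and functioning". The stated aim is "to determine if certain app features were more highly preferred or more linked to changes in functioning than others". No covariate, partial correlation or regression is named, and D11 does not say how change enters the correlation.

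The other outcome analysis in D11 is a pre-post comparison ("Paired-samples T tests will be used and effect sizes obtained"). It does not involve app use.

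Section D6.1 tells Open Trial parents that "they should use the app in whatever ways they wish", with as much or as little therapist support as the parties judge useful. It names the 20 Open Trial dyads as the main basis for substantive conclusions.

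Section D6.2 provides for "self-report questionnaires administered before (pretest) and after (post-test) the app usage period". Tables D6.2a and D6.2b list 9 parent and 9 youth scales of functioning or behavior given at both times, 18 in all. The baseline score of every such outcome is therefore in hand.

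**The concern.** Use is chosen, not assigned, so it may depend on how troubled the family was at the start. If it does, an unadjusted correlation mixes any effect of a feature with the starting level of the families who used it.

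Take a problem scale on which higher is worse, and suppose that families with higher baseline scores use a feature more. With change scores, regression to the mean makes those families appear to improve, so the feature looks helpful. With post scores, the same families are still worse at the end, so the feature looks harmful. If less severe families are the heavier users, both signs flip and the sizes stay the same.

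The stated purpose is to identify features that go with change in functioning. A feature could be named, or dropped, because of who used it, and the direction could turn on an analysis choice that D11 leaves open.

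**Working it through.** D11 gives no power, alpha or target correlation for this analysis, so there is no planned figure to reproduce.

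**Inputs from the documents.** N = 20 Open Trial dyads (D6.1); use self-selected (D6.1); baseline available for all 18 scales (D6.2).

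**Assumed inputs, not in the documents.** Correlation of use with baseline, rho = 0, 0.3 or 0.5; pre-post correlation, r = 0.6, with 0.5 to 0.8 as sensitivity; equal pre and post variances; no true effect of use; two-sided 5% test.

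**Case A: use follows the observed baseline score.**
- corr(use, change) = -rho × sqrt((1 - r)/2). At r = 0.6, sqrt(0.4/2) = 0.447, giving -0.13 (rho 0.3) and -0.22 (rho 0.5).
- corr(use, post) = rho × r, giving +0.18 and +0.30.
- Partial correlation given baseline = 0.

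Simulation at N = 20, r = 0.6:

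| Estimate | Mean r, rho 0.3 to 0.5 | False-positive rate |
|---|---|---|
| Use v change score | -0.13 to -0.22 | about 8-16% |
| Use v post score | +0.18 to +0.29 | about 12-25% |
| Baseline-adjusted | 0.00 | 5% |

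Over r = 0.5 to 0.8 and rho = 0.3 to 0.5, the rates are 6.7-18.6% for change scores and 9.6-42.9% for post scores. At rho = 0 all three estimates are unbiased, with rates of about 5%.

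**Case B: use follows true severity, which the scale measures with error.** Let q be the reliability of the scale, s the stability of true severity from pre to post, and rho the correlation of use with true severity.
- corr(use, change) = -rho × sqrt(q) × (1 - s) / sqrt(2(1 - qs)). This is zero when s = 1.
- Partial correlation given baseline = rho × sqrt(q) × s × (1 - q) / sqrt((1 - rho²q)(1 - q²s²)). This is above zero whenever q < 1 and rho and s are above zero.
- q = 0.6, s = 1, rho = 0.3: 0.3 × 0.775 × 0.4 / sqrt(0.946 × 0.64) = 0.12. For rho = 0.5: 0.155 / sqrt(0.85 × 0.64) = 0.21. Simulated at N = 20, the adjusted estimate averages +0.12 to +0.20 with 8-14% false positives; the change score averages 0.00 with 5%.
- q = 0.8, s = 0.7, rho = 0.5: change score -0.134 / sqrt(0.88) = -0.14, with about 9% false positives. Adjusted 0.0626 / sqrt(0.80 × 0.686) = +0.08, with about 6%.

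Over q = 0.6 to 0.9 and s = 0.7 to 1.0, the adjusted estimate has about 5-14% false positives.

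**Reading the two cases together.** Adjustment is exact in Case A. The change score is exact in Case B with stable severity. Neither is exact when true severity drifts. The raw post-score correlation was the worst or equal-worst choice in every scenario with a use-severity link; it equals the change score in size at r = 0.5 in Case A.

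**The case against.** Most of the case on the other side stands, and it limits the point.

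- **No stated link between severity and use.** A reader might infer that more severe families do use the app more, so that the planned correlations are spurious. The documents do not support this. Section D2 says "Youth are generally allocated to a particular level of service based on problem severity", which concerns service level and not app use. The bias is conditional on an association that may be absent.
- **The target is change.** The words "more linked to changes in functioning than others" point to a change score, so the post-score figures apply only if the analyst departs from that wording. That narrows the gap but does not close it: how change is computed is unspecified, and a change score is still exposed to regression to the mean.
- **Adjustment can itself mislead.** A reader might infer that adding the baseline score removes the problem and that the raw correlations can be discarded. Case B shows otherwise, and nothing in the documents tells us which case applies. This stands, and it is why the fix keeps both estimates.
- **D11 asks for a comparison between features.** If severity raised use of all features alike, the shift would be largely common to them and would mostly cancel in a ranking. The calculations model one use variable at a time, so bias in the ranking needs severity to affect features differently, a further assumption.
- **Limited consequence.** This is a small single-group open trial. D11 ties a decision threshold to the SUS only and does not call these correlations causal. The average biases at r = 0.6 (0.13 to 0.29) lie below the critical |r| of 0.444 at N = 20. Chance matters at least as much: 5 app features × 18 scales is 90 pairs, and 90 × 0.05 = 4.5 nominally significant results are expected with no effect anywhere, even with perfect adjustment.

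None of this supplies the missing specification, and naming features linked to change is a declared purpose of the analysis.

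**Conclusion.** The gap is real but moderate. D11 relates self-selected use to outcome without adjustment and without defining the outcome score, although every scale has a baseline. If use is correlated 0.3 to 0.5 with the observed baseline and pre-post correlation is 0.6, a nominal 5% test at N = 20 has a false-positive rate of about 8-16% with change scores and 12-25% with post scores, in opposite directions. These inputs are assumptions; with no use-severity association the excess is nil.

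The firm conclusions are that raw post-score correlations should not be used to identify features linked to change, and that the measure of change should be fixed in advance. The documents do not support a stronger claim, either that the links will be spurious or that baseline adjustment alone makes them sound.

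**What to change.** In D11:

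1. Define change as post-usage minus baseline score, and do not use raw post-score correlations to identify features linked to change.
2. For each feature-scale pair, report the association of feature use with the post-usage score adjusted for the same scale's baseline score (linear regression or partial correlation), with a 95% confidence interval. Put the use versus change-score correlation beside it.
3. Describe a feature as linked to change only if the two estimates agree, for example if they have the same sign and both intervals exclude zero. The rate at which both mislead together cannot exceed the smaller of the two separate rates. The price is some loss of power.
4. Label all these results exploratory and non-causal, and state how many pairs were examined. Adjustment for the scale's own baseline does not deal with differences in service intensity or therapist support.
5. Say that this analysis uses Open Trial dyads. Field Test parents "will be encouraged to use the app as much as possible over the next 2 weeks", so their use is not comparable.

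The core change (items 1 to 4) costs one or two sentences and one degree of freedom per model; item 5 adds a clause. No new data are needed. Where use is unrelated to baseline, adjustment also gains precision: residual variance relative to the change score is (1 + r)/2, or 0.80 at r = 0.6.

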***Preliminary Development of Blueprint.*** The app development team (Drs. [name], [name], and [name]) met in December, 2013 in New York City with Parsons School of Design Professor, [name], MS, for initial development of a conceptual blueprint. We then met again in Seattle, WA in February, 2014 to further refine the design blueprint and ensuring that it met the functional design requirements while simultaneously working for the real-demands/needs of our target end-users based on the case user profiles (described above).

***Iterative Development: From Blueprint to Build.*** Following completion of the design, we began the development of the app in detail moving from simple drawings and low-fidelity diagrams to a dynamic pre-build version that illustrates how the app will work and function when complete, including how the parent and youth apps “communicate” in real-time. Throughout all phases of development, we have individually interviewed target end-users, therapists, and more recently, stakeholders, to gain insights to improve usability and acceptability. Feedback has been overwhelmingly positive across groups. As hoped, user tests with youth and families has helped us identify those elements and paths that were confusing and required re-engineering of the design. Feedback from therapists and administrators has been helpful in identifying eventual barriers to use and implementation. Target end-users are enthusiastic to have the app available for use in real-world practice.

***The app and its features.*** The VillageWhere app assembles components of existing smartphone technology to allow parents to keep track of the youth’s behavior and send him or her reminders and rewards, and youth to see what the parent’s expectations are for him or her on a given day, get reminders to do things, and get praise or other rewards for doing the right thing. The features of VillageWhere for which beta versions currently exist and will be available for use in the present study include:

- 1) **Map.** Uses GPS function on youth’s smart phone to allow the parent to set up “geofences” denoting where the youth is and is not allowed to be at various times of day. The parent can always see where the youth is at a given moment, and can set up alerts to be notified if a youth leaves or enters a geofenced area.

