**App data generation.** Any app usage by parent or youth participant will result in the generation of information about type, duration, and other details of use (e.g., time of day) by the app itself (see measures section); these data will be captured on the server and will be deidentified. These data are substantive indicators critical for meeting one of the study's goals, namely, to determine whether and how (what features, etc.) real-world consumers are likely to use the app.

**Family app usage periods and daily satisfaction ratings.** The study will use 2 different app usage testing period lengths, depending on the timing of participant enrollment:

- **Field-Based Beta Testing Group** - the first 4-6 parent-youth participants will test the app for 14 days. The purpose of this phase is to ensure that the app is "bug free" and features perform as expected before it is subjected to a full initial open trial. Only four parent-youth dyads will participate in this phase if early users experience no or only

minor, easily-fixed glitches with app functioning. Five or six parent-youth dyads will participate if we determine that fixes to the app were substantial enough that the product needs to be retested with several additional participants before the open trial. The field-based testing group can be viewed as a pilot phase for the open trial. Except for the shorter testing period and different usage instructions (see next section), the procedures for this group will be identical to those in the open trial group (e.g., compensation, baseline and post-testing batteries, therapist involvement, etc.).

- **Open Trial Group** – Twenty parent-youth dyads will test the app for 45 days. Data obtained from this group will be the main basis upon which substantive conclusions about the app's success (the aims of this study) will be drawn.

Once each day during the testing period, the app will prompt each participant to answer three questions regarding his or her satisfaction with the app on that day. Participants will respond to the questions directly on their phones (within the app). Answering the questions will take less than 5 minutes. Data generated by these daily prompts will be stored on the app server. If during field-based beta testing users complain about the frequency being too high and too intrusive, we will reduce the frequency of collection (e.g., to twice each week) based on initial user feedback.

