## **E. PROTECTION OF HUMAN SUBJECTS**

### **E1. RISKS TO THE SUBJECTS**

#### *a. Human Subjects Involvement and Characteristics*

- Describe the proposed involvement of human subjects.

- Describe the characteristics of the subject population, including their anticipated number, age range and health status.

Three categories of human subjects will participate: 1) Parents of adolescents who are receiving mental health treatment, 2) adolescents receiving mental health treatment, and 3) therapists providing mental health treatment to parents and adolescents jointly. Participants will include at least 24 parents and 24 youth (at least 4 each in the field-based beta testing phase, 20 each in the Open Trial). Depending on problems encountered during the field test phase of the study, additional parents and youth might be needed to “debug” app problems prior to the open trial. The maximum number of parent and youth enrollees will not exceed 30 of each. Estimating therapist enrollment is difficult, because it is not yet known how many therapists will need to enroll in order to recruit a minimum of  $N = 24$  parent-youth dyads. We assume that a maximum  $N = 40$  enrolled therapists will be sufficient to recruit the parent-youth sample.

Parent and therapist age ranges will vary, but all will be adults (age 18 or older). Youth participants will range in age from 12-17 years old. All participants are expected to be physically healthy. In terms of mental health functioning, adolescent participants will be heterogenous, but all will have functional impairments sufficient to warrant their participation in either in-home or outpatient mental health treatment. Functional impairments may include internalizing symptoms (e.g., depressed mood, anxiety, social withdrawal), externalizing symptoms (e.g., oppositional behavior, drug or alcohol use), and failure to meet the developmental demands of their natural environments (e.g., to attend school, interact appropriately with peers, or refrain from criminal activity). A unifying factor across this heterogenous sample of adolescents is that all will be receiving family-oriented mental health treatment in which one goal is improved parental management of adolescent behavior.

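### D11 asks whether some app features are more linked to change than others, but names no comparison between features' correlations (minor, exploratory)

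*Combined protocol and SAP*

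**What the plan says.** D11 (Data Analysis) states the method in one clause: "Correlational analyses will link app usage data to participant satisfaction ratings and to measures of parent/youth behavior and functioning". The purpose follows at once: "to determine if certain app features were more highly preferred or more linked to changes in functioning than others". For this step D11 gives no contrast between correlations, no confidence interval, no model that holds several features together, and no significance level. The t-tests in D11 serve other questions: the parent-adolescent comparison on the usability scale, and pre-post change. D7.2 (App inquiries) adds an association of therapist support with usage and outcomes, again without a contrast.

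Five features are listed in Section C, after the words "The features of VillageWhere for which beta versions currently exist and will be available for use in the present study include": Map, Game Plan, Store, Our Progress and My Supports. D6.1 sets the main sample, "Twenty parent-youth dyads will test the app for 45 days", and says of it: "Data obtained from this group will be the main basis upon which substantive conclusions" are to be drawn. If field-test dyads were pooled in, Section E1 gives the bounds: "Participants will include at least 24 parents and 24 youth", and "The maximum number of parent and youth enrollees will not exceed 30 of each".

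**The concern.** To say that one feature is more linked to change than another is to say that two correlations differ. The matching null hypothesis is that they are equal. A correlation between a single feature and an outcome speaks to a different null, that this one correlation is zero. Setting such correlations side by side does not answer the comparative question. One of five sample correlations is always the largest, and a feature that clears a threshold beside one that misses it is not thereby shown to be more strongly linked.

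The five correlations also come from the same dyads and share the same outcome. They are therefore dependent, and the uncertainty of a difference cannot be judged from two separate correlations or their separate intervals.

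This is distinct from multiplicity. It arises with one outcome, when every feature is truly linked, and after the significance level has been corrected. At stake is whether the report can say that some features matter more than others, when the data may show only noise.

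**Working it through.** The plan gives no power, precision or effect size for these correlations, so there is no figure of its own to reproduce.

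**Inputs from the protocol.** Five features (Section C). n = 20 dyads in the open trial (D6.1). Upper bound n = 30 (Section E1).

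**Assumed inputs (not in the protocol).** A common true correlation rho of each feature's use with one outcome, from 0 to 0.6. Correlation between features from 0.3 to 0.7. Multivariate normal data. Two-sided 5% level wherever significance is used.

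**Step 1: precision of one correlation.** The 95% interval on Fisher's scale is tanh(atanh r ± 1.96/√(n − 3)). For r = 0.3 and n = 20: atanh 0.3 = 0.310 and 1.96/√17 = 0.475, so the interval is −0.16 to 0.66. The smallest |r| significant at 5% is t/√(t² + n − 2) = 2.101/√(2.101² + 18) = 0.444.

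**Step 2: five equally linked features.** Simulation with 20,000 studies per setting, n = 20:

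| Quantity | Result |
|---|---|
| Median gap, largest minus smallest r (rho 0 to 0.6) | 0.21 to 0.44 |
| Share of studies with gap above 0.2 (rho 0 to 0.6) | 56% to 95% |
| Some features significant at 5%, others not: rho 0 to 0.2 | 15% to 44% |
| Same, rho 0.3 to 0.5 | 44% to 82% |
| Same, rho 0.6 | 36% to 55% |

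The last three rows use a 5% rule that D11 does not state for these correlations. At n = 30 the gap still exceeds 0.2 in 46% to 90% of studies (rho 0 to 0.5).

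**Step 3: a direct comparison.** Williams' test for two correlations r1 and r2 that share an outcome, with r12 the correlation between the two features:

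T = (r1 − r2) √{(n − 1)(1 + r12) / [2((n − 1)/(n − 3))D + m²(1 − r12)³]}, on n − 3 df, where D = 1 − r1² − r2² − r12² + 2·r1·r2·r12 and m = (r1 + r2)/2.

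Example with observed r1 = 0.5, r2 = 0.2, r12 = 0.5 and n = 20:
- D = 1 − 0.25 − 0.04 − 0.25 + 0.10 = 0.56, and m² = 0.1225.
- Numerator: 19 × 1.5 = 28.5.
- Denominator: 2 × (19/17) × 0.56 + 0.1225 × 0.125 = 1.252 + 0.015 = 1.267.
- T = 0.3 × √(28.5/1.267) = 0.3 × 4.74 = 1.42, against a critical value of 2.11 on 17 df.

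The first feature is significant (0.5 > 0.444) and the second is not (0.2 < 0.444), yet the two cannot be told apart.

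In simulation, Williams' test rejects for an equally linked pair in about 5% of studies, as it should.

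**Step 4: power of the direct comparison.** n = 20, correlation between features 0.3 to 0.5. Five features make 5 × 4/2 = 10 pairs, so Bonferroni uses 0.05/10 = 0.005:

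| True correlations | One pair, unadjusted | Bonferroni over 10 pairs |
|---|---|---|
| 0.6 v 0 | 71% to 88% | 35% to 59% |
| 0.5 v 0 | 50% to 67% | 17% to 31% |
| 0.5 v 0.2 | 21% to 28% | 4% to 7% |

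**The case against.** The best defence is that this is one exploratory sentence in a single-group preliminary study. D11 sets no significance rule for these correlations, and correlational analysis is a broad term that does not exclude a contrast or a joint model. The usability threshold of 3.5 is the only stated rule for further refinement of the app. A direct comparison would have little power, so formal testing may add little beyond softer wording.

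Much of this stands. It makes the point minor, and it is why intervals and descriptive wording should come before adjusted pairwise tests. It does not remove the gap: the stated purpose is comparative and no comparison is named. Low power strengthens the case for saying plainly when features cannot be told apart.

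A reader might infer two stronger things that the documents do not support:

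- *That equally linked features will usually be split into significant and non-significant.* This needs a 5% rule that D11 does not state. Even with one, it depends on the unknown rho: at 0 to 0.2 a mixed pattern occurs in 15% to 44% of studies. For any one given pair at n = 20 (correlation between features 0 to 0.5), discordant significance occurs in 8% to 52%.
- *That a useful feature could be dropped by chance.* No passage ties keeping or dropping a feature to these correlations. D11 takes preferred features from descriptive usage data, and suggestions for improvement from exit interviews.

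**Conclusion.** The concern holds as a minor point. D11 poses a question about differences between features and names only correlations of usage with outcomes, which do not assess those differences. With 20 dyads and five equally linked features, chance alone typically separates the largest and smallest correlations by 0.21 to 0.44. A ranking read from their sizes would therefore not be evidence that features differ.

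These figures rest on assumed true correlations, assumed correlations between features, normal data and a single outcome. The logical gap rests on none of them.

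The consequence is confined to exploratory statements that rank features. The usability criterion and the pre-post tests are unaffected.

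**What to change.** In D11:

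1. Report each feature's correlation with change, with a 95% confidence interval, and label it descriptive.
2. Base any statement that one feature is more linked than another on an interval for the difference between the two dependent correlations, from a bootstrap that resamples whole dyads. A Williams or Steiger test is an alternative.
3. Where that interval includes zero, state that the features cannot be distinguished.
4. Say in advance whether these comparisons are adjusted over the 10 feature pairs.

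If the team does not want to compare features formally, it can instead reword the aim as a description of each feature's association and drop the comparative claim.

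The change needs a few lines of code, one or two sentences in D11, and no new data. The real cost is that few features will be singled out. As the power table shows, one unadjusted pair is likely to be separated only when the true gap is large, and with adjustment even 0.6 v 0 reaches only about 35% to 59%.
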